6.2 IMPORTANT PROTOCOL DEVIATIONS

Data discrepancies and deviations from the CTP will be identified for all treated subjects.

Section 7.3 of the CTP: *Important protocol deviations (iPDs) categories will be specified in the IQRMP, iPDs will be identified no later than in the Report Planning Meeting, and the iPD categories will be updated as needed.*

Consistency check listings (for identification of deviations of time windows) and a list of protocol deviations (e.g. deviations in drug administration, in blood sampling times, etc.) will be provided to be discussed at the Report Planning Meeting (RPM). At this meeting, all manual deviations identified at the sites by the CRAs and deviations too complex to program will be reviewed by the trial team to decide which are considered important. For definition of important protocol deviations (iPD), and for the process of identification of these, refer to the Boehringer Ingelheim (BI) SOP "Identify and Manage Important Protocol Deviations (iPD)" ([2](#)).

If any iPDs are identified, they are to be summarised into categories and will be captured in the RPM minutes via an accompanying Excel spreadsheet ([3](#)). Categories which are considered to be iPDs in this trial are defined in the integrated quality and risk management plan (IQRMP). If the data show other iPDs, the definition in the IQRMP will be supplemented accordingly by the time of the RPM.

The iPDs will be summarised and listed.

6.3 SUBJECT SETS ANALYSED

- **Treated set (TS):**

This subject set includes all subjects who were dispensed study medication and were documented to have taken at least one dose of investigational treatment.

This is the full analysis set population in the sense of ICH-E9 (1). It is used for demographics, baseline characteristics, and safety analyses.

The ECG analyses are performed on the TS, except for the exposure-response analyses, which are performed on the ECGPCS defined below.

Section 7.3 of the CTP: *Plasma concentration data and parameters of a subject will be included in the statistical pharmacokinetic (PK) analyses if they are not flagged for exclusion due to a protocol deviation relevant to the evaluation of PK (to be decided no later than in the Report Planning Meeting) or due to PK non-evaluability (as revealed during data analysis, based on the criteria specified below). Exclusion of a subject's data will be documented in the CTR.*

Relevant protocol deviations may be

- *Incorrect trial medication taken, i.e., the subject received at least one dose of trial medication the subject was not assigned to*
- *Incorrect dose of trial medication taken*
- *Use of restricted medications*

Plasma concentrations and/or parameters of a subject will be considered as non-evaluable, if for example

- *The subject experienced emesis that occurred at or before two times median t_{max} of the respective treatment (Median t_{max} is to be determined excluding the subjects experiencing emesis),*
- *Missing samples/concentration data at important phases of PK disposition curve.*

Plasma/urine concentration data and parameters of a subject which is flagged for exclusion will be reported with its individual values but will not be included in the statistical analyses.

- **Pharmacokinetic parameter analysis set (PKS):**

The pharmacokinetic parameter analysis set (PKS) includes all subjects from the TS receiving BI 1358894 who provide at least one PK endpoint that was not excluded according to the description above.

It is used for assessment of dose proportionality and the descriptive analyses of PK parameters.

The descriptive analysis of PK concentrations will be based on the ADS ADPC. The descriptive and model based analysis of PK parameters will be based on the ADS ADPP.

- **ECG Pharmacokinetic Concentration Set (ECGPCS):**
This subject set includes all subjects from the TS for whom at least one pair of a valid drug plasma concentration of BI 1358894 and a corresponding (i.e. time-matched) ECG endpoint to be used in the exposure-response analyses was provided. For placebo subjects, the plasma concentration is set to zero and hence always considered as valid. The decision whether a time deviation between PK blood sampling and ECG recording is acceptable (and thus whether the pair of values will be used) is to be made no later than at the RPM before data-base lock.

Table 6.3: 1 Analysis sets for endpoints/data description

Endpoint/data description	Analysis set		
	TS	PKS	ECGPCS
Primary and further safety endpoints (incl. ECG)	X		
ECG endpoints and plasma concentrations used in exposure-response analysis			X
Secondary PK endpoints		X	
Demographic/baseline data	X		
Important protocol deviations		X	
Disposition		X	

6.5 POOLING OF CENTRES

This section is not applicable, because the study was performed in only one centre.

6.6 HANDLING OF MISSING DATA AND OUTLIERS

Handling of missing data and outliers will be performed as described in the CTP, Section 7.5.

The only exceptions where imputation might be necessary for safety evaluation are AE dates. Missing or incomplete AE dates are imputed according to BI standards.

Missing data and outliers of PK data are handled according to BI standards (see 001-MCS-36-472_RD-01) (4).

If single cardiac cycles of an ECG (out of the generally four) are missing, the arithmetic mean for this single ECG will be computed with the reduced (1, 2 or 3) number of cardiac cycles.

If replicate ECG recordings are missing, the arithmetic means per time point will be computed with the reduced number (1 or 2) of recordings.

For the classification of the on treatment QTc/QT intervals into “no new onset” / “new onset” categories, a missing value is obtained only in case that

- (i) all on treatment values are missing and
- (ii) the baseline value is less than or equal to 500 msec, or missing.

If condition (i) is fulfilled but the baseline value is greater than 500 msec, this case will be categorized as ‘no new onset’. If baseline is missing and the maximum on treatment QTc interval is greater than 450 msec (or 500 msec for QT interval, respectively), this is classified as a ‘new onset’ in the respective category. If baseline is missing and the maximum QTc interval is less than or equal to 450 msec (or 500 msec for QT interval, respectively), this will be categorized as ‘no new onset’. If baseline is missing, a QTc/QT interval > 500 msec at any time on treatment will be a notable finding. In case of a missing qualitative ECG finding at baseline, a finding observed on treatment will be categorized as ‘new onset’.

For placebo subjects, the missing plasma concentration values will be replaced by 0 for the exposure-response analyses. For subjects on active drug, missing plasma concentration values with ‘BLQ’ in the comment field will be replaced by $\frac{1}{2}$ LLOQ (post treatment values) or by 0 (predose values).

6.7 BASELINE, TIME WINDOWS AND CALCULATED VISITS

The baseline value is defined as the last measurement before administration of BI 1358894 or Placebo.

Section 6.1 of the CTP: *Exact times of measurements outside the permitted time windows will be documented. The acceptable time windows for screening and the end of trial examination are provided in the CTP Flow Chart.*

Study measurements and assessments scheduled to occur ‘before’ trial medication administration on Day 1 are to be performed and completed within a 2 h-period prior to the trial drug administration except PK sample. A blank sample for PK will be collected within 3 h before drug administration.

The acceptable deviation from the scheduled time for vital signs, orthostatic testing and ECG will be ± 10 min and laboratory tests will be ± 30 min for the first 4 h after trial drug administration and ± 30 min thereafter.

[...]

Adherence to time windows will be checked via the consistency check listings at the RPM.

Unscheduled measurements of laboratory data or vital signs will be assumed to be repeat measurements of the most recent scheduled measurement (e.g. for follow-up or confirmation of a particular value). Therefore, unscheduled measurements will be assigned to the planned time point of the previous scheduled measurement.

There will be a centralised evaluation of the 12-lead ECG recordings at the time points and for the ECG recordings specified in the [Table 6.7: 1](#) below:

Section 5.2.4.1 of the CTP: *Triple ECGs will be recorded (within 180 sec) at all-time points on Day 1 to Day 3 (48 h) for Dose Groups 1 and 2 or on Day 1 to Day 7 (144h) for Dose Group 3. At all remaining time points, single ECGs will be recorded.*

Table 6.7: 1 Time schedule of 12-lead ECG recordings

Visit	Day	Planned time [hh:mm] (relative to drug administration)	Study phase	Central evaluation
1	-28 to -1		Screening	NA
2	1	-01:00	Baseline	all 3 single ECGs of the triplicate
		00:30		first of three replicate ECG
		01:00		first of three replicate ECG
		01:30		first of three replicate ECG
		02:00		first of three replicate ECG
		03:00		first of three replicate ECG
		04:00		first of three replicate ECG
		05:00		first of three replicate ECG
		06:00		first of three replicate ECG
		08:00	On treatment	first of three replicate ECG
		12:00		first of three replicate ECG
	2	16:00		first of three replicate ECG
		24:00		first of three replicate ECG
		34:00		first of three replicate ECG
	3	48:00		first of three replicate ECG
	4	72:00**		first of three replicate ECG**
	5	96:00**		first of three replicate ECG**
	6	120:00**		first of three replicate ECG
	7	144:00**		first of three replicate ECG
3	10 to 14* 29 to 33**		End of trial examination	NA

*for dose groups 1 and 2

**for dose group 3

The baseline value of an ECG variable is defined as the mean of the triplicate ECG measurements prior to drug administration.

Section 5.2.4.1 of the CTP: A centralised evaluation (during study or post study) of all 12-lead ECGs recorded on Day 1 to Day 3 (48h) for Dose Groups 1 and 2 or on Day 1 to Day 7

(144h) for Dose Group 3 will be performed by an independent ECG laboratory. This analysis will include the determination of cardiac axis (automatic evaluation based on a validated GE-12-SL-algorithm or equivalent) as well as the intervals RR, PR, QRS and QT measured semi-automatically. With the exception of the first triple ECG (used as baseline before the drug administration), only the first of the three replicate ECGs at a single assessment time will be evaluated. [...].

For the exposure response analyses, pairs of ECG variables and corresponding plasma concentrations will be built using the same planned time points, e.g. HR change from baseline and the plasma concentration measured at planned time 0:30 will build one pair. Whether a time deviation between PK blood sampling time and corresponding ECG recording is too big and the pair has to be excluded from the analysis will be decided no later than at the RPM. This critical time deviation depends on the PK properties. When plasma concentrations are expected to change only little around a given time point, the acceptable time deviation between ECG recording and PK blood sampling may be bigger.

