Proprietary confidential information © 2019 Boehringer Ingelheim International GmbH or one or more of its affiliated companies

Dose Group 3 (200 mg)

Visit	Day	Planned time (relative to drug administration [h:min])	Approximate clock time of actual day [h:min]	Event and comment	Safety laboratory 	PK blood	PK urine 	Orthostatic testing	Visual analogue scale	C-SSRS	Neurological Examination	12-lead ECG	Continuous ECG monitoring	Vital signs (BP, PR, RR)	Questioning for AEs and concomitant therapy 
1	-28 to -1			Screening (SCR) 	x			x	x	x	x	x		x	
2	-1	-24:00 	09:00	Ambulatory visit	x 										x
		-12:00	21:00	Admission to trial site	x 										
	1	-1:00	08:00	Allocation to treatment 	x 	x 	x 	x 	x 			x 		x 	x 
		-0:30	08:30	High-calorie, high-fat breakfast											
		0:00	09:00	Drug administration 			▲						▲		
		0:10	09:10			x									
		0:20	09:20			x									
		0:30	09:30			x						x 		x	x
		1:00	10:00			x						x 		x	x
		1:30	10:30			x						x 		x	x
		2:00	11:00	240 mL fluid intake		x			x			x 		x	x
		2:30	11:30			x									
		3:00	12:00			x		x				x 		x	x
		4:00	13:00	240 mL fluid intake, thereafter lunch 	x	x	+		x			x 	▼	x	x
		5:00	14:00			x						x 		x	x
		6:00	15:00			x						x 		x	x
		7:00	16:00			x									
		8:00	17:00			x	+		x			x 		x	x
		10:00	19:00	Dinner 		x									
		12:00	21:00			x	+					x 		x	x
	2	16:00	01:00			x						x 		x	
		24:00	09:00	Breakfast 	x	x	+		x			x 		x	x
		34:00	19:00			x			x			x 		x	x
	3	48:00	09:00	Breakfast 		x	+		x			x 		x	x
	4	72:00	09:00	Breakfast 		x	+					x 		x	x
	5	96:00	09:00	Breakfast 	x	x		▼				x 		x	x
	6	120:00	09:00	Breakfast 		x						x 		x	x
	7	144:00	09:00	Breakfast  , confirmation of fitness  , Discharge from trial site		x			x	x	x	x 		x	x
	9	192:00	09:00	Ambulatory visit		x								x	x
	11	240:00	09:00	Ambulatory visit		x								x	x
	15	336:00	09:00	Ambulatory visit		x								x	x
	22	504:00	09:00	Ambulatory visit		x								x	x

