#### **5.2.3 Safety laboratory parameters**

For the assessment of laboratory parameters, blood and urine samples will be collected by the trial site at the times indicated in the Flow Chart after the subjects have fasted for at least 10 h except 4h on Day 1. For retests, at the discretion of the investigator or designee, overnight

fasting is not required. The parameters that will be determined are listed in Tables 5.2.3: 1 and 5.2.3: 2. Reference ranges will be provided in the ISF.

Manual differential white blood cell count or urine sediment examinations will only be performed if there is an abnormality in the automatic blood cell count and clinically relevant in the opinion of the investigator or in the urinalysis, respectively.

Table 5.2.3: 1 Routine laboratory tests

Functional lab group	Test name
Haematology	Haematocrit Haemoglobin Red blood cell count (RBC) Reticulocyte count White blood cell count (WBC) Platelet count Erythrocyte Sedimentation Rate (ESR) Neutrophils, eosinophils, basophils, monocytes, lymphocytes
Automatic WBC differential (relative and absolute)	
Manual differential WBC (if automatic differential WBC is abnormal and clinically relevant in the opinion of the investigator)	Polymorphnuclear neutrophils (segs), band neutrophils (stabs), eosinophils, basophils, monocytes, lymphocytes
Coagulation	Activated partial thromboplastin time (aPTT) Prothrombin time (Quick's test and INR) Fibrinogen
Enzymes	Aspartate transaminase (AST/GOT) Alanine transaminase (ALT/GPT) Alkaline phosphatase (AP) Gamma-glutamyl transferase (GGT) Creatine kinase (CK) CK-MB, only if CK is elevated Lactate dehydrogenase (LDH) Lipase Amylase
Hormones 	Thyroid stimulating hormone (TSH) fT3, fT4
Substrates 	Plasma glucose Creatinine Total bilirubin Direct bilirubin Total protein Protein electrophoresis (only at screening examination) 
 
Albumin
 
Alpha-1-Globulin
 
Alpha-2-Globulin
 
Beta-Globulin
 
Gamma-Globulin
 
 C-Reactive Protein (CRP) Uric acid Total cholesterol Triglycerides

Table 5.2.3: 1 Routine laboratory tests (cont.).

Functional lab group	Test name
Electrolytes	Sodium Potassium Calcium
Urinalysis (Stix)	Urine nitrite Urine protein Urine glucose Urine ketone Urobilinogen Urine bilirubin Urine erythrocytes Urine leukocytes Urine pH

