### **6.2.3      End of Trial period**

For AE assessment, laboratory tests, recording of ECG and vital signs, physical examination, Bowdle visual analogue scales and suicidality assessment (C-SSRS) during the end of trial period, see Sections [5.2](#).

Subjects who discontinue treatment before the end of the planned treatment period should undergo the End of Trial Visit.

All abnormal values (including laboratory parameters) that are assessed as clinically relevant by the investigator will be monitored using the appropriate tests until a return to a medically acceptable level is achieved. (S)AEs persisting after a subject's End of Trial Visit must be followed until they have resolved, have been sufficiently characterised, or no further information can be obtained.

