7.8.2 Laboratory data

The analyses of laboratory data will be descriptive in nature and will be based on BI standards.

Laboratory data will be analysed qualitatively via comparison of laboratory data to their reference ranges. Values outside the reference range as well as values defined as possible clinically significant will be flagged in the data listings.

Clinically relevant findings in laboratory data will be reported as baseline conditions (at screening) or as AEs (during the trial) if judged clinically relevant by the investigator, and will be analysed as such.

It is the investigator's responsibility to decide whether a lab value is clinically significant abnormal or not (at the RPM at the latest).

Descriptive statistics of laboratory data will be calculated by planned time point based on the worst value of the subject at that planned time point (or assigned to that planned time point).

The mean normalised values and SD over time for all laboratory parameters, except for parameters that are measured at a single time point will be displayed graphically. The time span is from baseline to post examination.

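### Unscheduled laboratory results are carried back to the previous scheduled time with no time limit, so at 200 mg a worse result from up to 24 to 28 days later would be tabulated as the 96 h value

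*SAP*

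**What the plan says.** SAP 6.7 sets the assumption: "Unscheduled measurements of laboratory data or vital signs will be assumed to be repeat measurements of the most recent scheduled measurement". It names follow-up and confirmation as examples and draws the consequence: "Therefore, unscheduled measurements will be assigned to the planned time point of the previous scheduled measurement". It gives no longest interval beyond which this stops applying.

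SAP 7.8.2 calculates laboratory descriptive statistics per planned time "based on the worst value of the subject at that planned time point (or assigned to that planned time point". Vital signs, under SAP 7.8.3, use the last value instead.

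The protocol foresees unscheduled laboratory samples. Under Protocol 6.2.3, clinically relevant abnormal values "will be monitored using the appropriate tests until a return to a medically acceptable level is achieved". Protocol 5.2.6.1.5 foresees an unscheduled blood test when symptoms suggest hepatic injury and no liver results are available. Protocol 5.2.3 also provides for retests.

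**The concern.** Treating an off-schedule sample as a repeat is reasonable when it is taken hours after the scheduled one. Without a limit, the rule also covers a sample taken weeks later, which is a new observation. Combined with the worst-value rule, the later result does more than sit beside the scheduled one: if it is worse, it replaces it under the earlier time label.

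What is at stake is the time axis of the laboratory tables in the highest dose group. A change that first appears in the third or fourth week would be shown as a 96 h change. PK sampling in that group runs to 672 h, and SAP 7.8.1 quotes the residual effect period as not known, so the timing of a laboratory change relative to exposure is informative. The comparison with placebo is also uneven. All six active 200 mg subjects face the long gap, but only two of the six pooled placebo subjects do.

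**Working it through.** The documents give no figure of their own on this point, so the check is schedule arithmetic plus one illustration.

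**Inputs**
- Dose Group 3 Flow Chart: post-dose safety laboratory at 4 h, 24 h and 96 h. The Day 5 row reads "5 96:00 09:00 Breakfast 3 x x", with marks for both safety laboratory and PK blood.
- The next row reads "6 120:00 09:00 Breakfast 3 x". Its single mark is for PK blood. The rows for 144, 192, 240, 336, 504 and 672 h likewise have no safety laboratory mark.
- Footnote 11 (confirmation of fitness, Day 7) lists no safety laboratory.
- The next scheduled safety laboratory is at the end of trial, Day 29 to 33. In Dose Groups 1 and 2 the end of trial is Day 10 to 14.

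**Day to hour conversion**

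Hours = (Day − 1) × 24. This returns the Flow Chart's own pairs: Day 5 = 96 h, Day 7 = 144 h, Day 15 = 336 h, Day 22 = 504 h, Day 29 = 672 h.

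**Length of the gap after 96 h**

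| Group | End-of-trial day | Hours | Minus 96 h | Days |
|---|---|---|---|---|
| 3 | 29 | 672 | 576 | 24 |
| 3 | 33 | 768 | 672 | 28 |
| 1 and 2 | 10 | 216 | 120 | 5 |
| 1 and 2 | 14 | 312 | 216 | 9 |

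The last two rows assume that 96 h is the last in-house laboratory in Dose Groups 1 and 2, because the columns of that table are broken in the text available. An unscheduled result can be carried back by anything up to the length of the gap.

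**Influence of one value (assumed ALT figures)**

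Six active subjects all have 20 U/L at the scheduled 96 h sample, so the mean is 20. One has an unscheduled 150 U/L on Day 11 (240 h, six days later). The rule puts 150 at 96 h: (5 × 20 + 150) / 6 = 250 / 6 = 41.7. The tabulated 96 h mean rises by 21.7 U/L, although no subject had a raised value at 96 h.

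**Comparison with the plan's other rules**
- SAP 6.7 allows scheduled laboratory samples a deviation of ±30 min.
- Protocol 5.2.4.1 also assigns unscheduled ECGs to the prior scheduled time, but excludes them from the statistical analysis of interval lengths.
- SAP 6.7 allows ECG and concentration pairs to be dropped when their times differ too much.
- The Report Planning Meeting check in SAP 6.7 covers adherence to time windows, and an unscheduled sample has no window.

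**The case against.** The strongest reply is that the mis-dating is conditional. It needs an unscheduled sample in the gap, and that sample must be worse than the scheduled one. On the main follow-up route, an abnormal value is tracked until it settles, so the worst value is usually the scheduled one and nothing is replaced. This stands. The exposure is to a new or worsening late abnormality found off schedule, such as a symptom-driven hepatic test.

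It is also fair that worst-value tabulation is a conservative choice in a descriptive trial, that SAP 7 tabulates median and maximum as well (20 and 150 in the illustration), and that SAP 7.8.2 defers to sponsor standards not available here, which might set a limit. The maximum reveals the outlier but not its date, and the documents themselves state no limit.

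A reader might infer more, and the documents do not support it:
- **Wrong causality or onset.** Causality is judged per event (Protocol 5.2.6.1.7), and AEs are assigned by recorded onset time (Protocol 7.3.4). Neither uses this table.
- **A general inflation of the 200 mg mean through retesting.** The size depends on why samples are repeated. For independent normal values, the expected gain from one retest after a first value x (in SD) is φ(x) − x(1 − Φ(x)): 0.083 SD at x = 1 and 0.008 SD at x = 2. Staff are also blinded to active or placebo within a dose group, so retesting confined to active subjects cannot be presumed. Nor is worst always upward; for haemoglobin it may be the low direction.
- **Distorted mean plots.** This is possible, but SAP 7.8.2 does not say which value per time point the plots use.

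**Conclusion.** The point holds as a wrong time label in the by-time laboratory statistics. As written, the two SAP rules together would report an unscheduled result as the 96 h value whenever it falls in the gap and is worse than the scheduled sample. The greatest displacement at 200 mg is 24 days if the end of trial is on Day 29 and 28 days if it is on Day 33. In Dose Groups 1 and 2 it is about 5 to 9 days, on the stated assumption.

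With six active subjects, one displaced value can dominate a mean; the ALT figures only illustrate this. How often it would happen cannot be estimated from the documents.

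No abnormal result is lost: individual values are listed, clinically relevant findings are reported as AEs, and the primary endpoint does not use this table. The point is minor, but worth correcting because the correction is cheap.

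**What to change.** In SAP 6.7, limit assignment to the previous scheduled time to unscheduled laboratory samples taken within a short, stated window after it. The sponsor should choose the length and write it down. In SAP 7.8.2, exclude later unscheduled samples from the by-time statistics, list them at their actual day, and include them in a separate table of each subject's worst on-treatment value. State also which value per time point the mean plots use. The worst-value rule can stay for genuine short-interval repeats; dropping it there would be a matter of preference.

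The cost is a few sentences of SAP text and one extra table, with no change to trial conduct. The downside is that the by-time table no longer carries every worst value; the added table does.
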